7.1.3 Q-Interactive

Q-Interactive is the digital, cloud based platform used to administer cognitive assessments on a one-on-one basis using iPads in an app called Assess - The WISC-V will be administered using this method. One iPad is used by the researcher to view test instructions, score and record responses, and control visual stimuli; the second iPad is used by the participant to respond to stimuli. Test data is securely uploaded to Pearson's servers. The Q-interactive central is used for generating users and organising, reviewing, archiving, and exporting test results. Data will be transcribed from Q-interactive into the Medrio EDC by researchers based at recruiting sites.

7.2 Data security

7.2.1 Medrio and KCTU Randomisation System

The CI or delegate will request usernames and passwords from the KCTU for Medrio EDC/ePRO and Randomisation System. System access will be strictly restricted through user-specific passwords to the authorised research team members. It is a legal requirement that passwords to the randomisation system are not shared, and that only those authorised to access the system are allowed to do so. If new staff members join the study, a user-specific username and password must be requested via the CI or delegate (e.g., Trial Manager) from the KCTU team and a request for access to be revoked must be requested when staff members leave the project. Study site staff experiencing issues with system access or functionality should contact the Trial Manager in the first instance.

Participant initials and date of birth will be entered on the randomisation system. No data will be entered onto the randomisation system unless a participant has signed a consent form to participate in the trial.

7.2.2 Q-Interactive

Q-interactive adheres to strict data security standards to protect personally identifiable information (PII) and sensitive assessment data. Data is encrypted both in transit and at rest using industry-standard encryption protocols. User authentication requires strong credentials, and sessions are timed to log out automatically after periods of inactivity. Pearson complies with HIPAA, FERPA, and The electronic version of this document is the latest version. It is responsibility of the individual to ensure that any paper material is the current version. Printed material is uncontrolled documentation.

other relevant data protection regulations to ensure that clinical information is handled in a secure and compliant manner. Data centres hosting Q-interactive services are certified under recognized security frameworks such as ISO 27001 and SOC 2. The system supports role-based access and user permissions to ensure that data may only be accessed and managed by authorised personnel. Participants' date of birth, study PIN and birth-registered sex will be entered into the system following confirmation and documentation of informed consent.

7.3 Data quality processes

7.3.1 Medrio EDC

At the database design stage, validations will be programmed into the systems to minimise data entry errors by querying the data entered in real time with sites.

The CI team will undertake appropriate reviews of the entered data, in consultation with the project analyst, where appropriate for the purpose of data cleaning and will request amendments to the Medrio EDC system data as required. No data will be amended independently of the study site responsible for entering the data.

Site staff will respond to data queries within the EDC as required. During site monitoring visits, the CRA will raise any queries with sites via the Source Data Verification (SDV) function.

The KCTU will provide the study team with a Data Management Plan (DMP) for Medrio EDC for filing in the TMF.

7.3.2 KCTU Randomisation System

The CI team will undertake appropriate reviews of the entered data, in consultation with the project analyst for the purpose of data cleaning. No data can be amended in the system, however CI or delegate (e.g., Trial Manager) may request King's Clinical Trials Unit to add notes against individual subject entries to clarify data entry errors.

The KCTU will provide the study team with a DMP for the KCTU randomisation system once the system is made live.

7.3.3 Q-Interactive

Q-interactive has built-in checks to reduce scoring errors and standardise administration across users. The system automatically scores responses in real time and flags inconsistencies or incomplete data entries for review. Regular system updates and calibration procedures help preserve the accuracy of test materials and scoring. Digital administration minimises human error and ensures that data collected adheres to standardised protocols, enhancing the reliability and comparability of results.

7.4 Database lock

7.4.1 Medrio EDC

At the end of the trial, the site PIs will review all the data for each participant in the Medrio EDC system and provide electronic sign-off to verify that all the data are complete and correct.

The Trial Manager will confirm all checks are complete and all monitors queries have been resolved prior to database lock. At this point, with the agreement of the Senior Statistician, all data can be formally locked for analysis.

When the final data extract is requested, KCTU will remove all data entry user access prior to data extract and will retain only 'monitor' access for site PI's and other relevant individuals.

Upon request, KCTU will provide a copy of the final exported dataset to the CI in .csv format and the CI will onward distribute to sites as appropriate. Once sites have received copies of their individual datasets and confirmation of receipt has been received, the Trial Manager will request that all user access is removed from the Medrio EDC system. A copy of the dataset will be stored in the TMF at the end of the study.

7.4.2 KCTU Randomisation System

Upon request, KCTU will provide a copy of the final exported dataset to the CI in .csv format and the CI will onward distribute as appropriate.

7.4.3 Q-Interactive

Q-interactive features a database lock mechanism. Once an assessment session is finalized and uploaded to the Central platform, the data becomes read-only to prevent unauthorized alterations. This ensures an auditable, tamper-proof record of the session, supporting both clinical accountability and legal defensibility. In cases where data corrections are necessary, system administrators must follow defined procedures that log all changes and retain version histories for compliance and traceability.

At the end of the trial, assessment records will be exported from the Q-interactive platform as .csv files for storage. Once the dataset has been confirmed by the central PATHWAYS team, all relevant records from Q-interactive will be deleted.

7.5 MRI data management and storage (CONNECT)

MR images will be stored (pseudo-anonymised) on the Neuroimaging Analysis Network hosted at the Centre for Neuroimaging Sciences at KCL. This is a secure, password-protected dedicated server behind an institutional firewall with automated backups and archiving options. Access to the server will only be made possible following study-specific and data governance training and with authorisation from the

The electronic version of this document is the latest version. It is responsibility of the individual to ensure that any paper material is the current version. Printed material is uncontrolled documentation.

Cl. Data may also be stored on King's secured e-Research's Computational Research, Engineering and Technology Environment (CREATE).

8 Summary of known and potential risks of Triptorelin

Administration of Triptorelin for this study is not anticipated to induce any potential risk other than the known potential side effects listed below. Both CYP and adult profiles of side effects have been included as use of GnRHa for puberty suppression in transgender and gender diverse people is off-license, therefore consideration of all possible side effects will be required. Although there is no age specific information with regards to prevalence of side effects, Triptorelin is also used in the treatment of precocious puberty in children with an onset before 8 years in girls and 9 years in boys, and the SmPC was used to include known adverse reactions in this population (please refer to the most up to date SmPC). The same doses will be used in older children. The following adverse reactions have been noted with Triptorelin:

8.1 Side effects commonly reported

The following side effects are known to be commonly reported to Endocrinology Clinicians that have prescribed Triptorelin for those under the age of 18 years with a diagnosis of “Gender Incongruence” or “Gender Dysphoria” for the indication of puberty suppression. These have been collated from the expert endocrine panel as previously defined.

Common side effects reported clinically include unexpected PV bleeding (commonly referred to as spotting), hot flushes, increased perspiration, weight gain, injection site pain, mood changes, interrupted sleep, low mood, dizziness, fatigue, cyclic menstrual-like pelvic discomfort, breast tenderness, nausea, headache, reduced libido, and loss of spontaneous erections.

Common side effects reported of a subcutaneous injection are localised pain, swelling, sterile abscess, allergic reaction, muscular pain, induration and erythema.

8.2 Common side effects of Triptorelin

Common is defined as per BNF and BNFc standards with a frequency of between 1 in 100 to 1 into 10.

In under 18's, common side effects that have been reported are depression and altered mood.

In adults, common side effects are anxiety, asthenia, depression, diabetes mellitus, dizziness, dry mouth, embolism, gastrointestinal discomfort, gynaecomastia, haemorrhage, headache, hot flushes, hyperhidrosis, hypersensitivity, hypertension, joint disorders, menstrual cycle irregularities, altered mood, muscle complaints, nausea, oedema, ovarian and fallopian tube disorders, pain, painful sexual

The electronic version of this document is the latest version. It is responsibility of the individual to ensure that any paper material is the current version. Printed material is uncontrolled documentation.

intercourse, pelvic pain, sexual dysfunction, skin reactions, sleep disorders and weight changes.

8.3 Uncommon and rare side effects of Triptorelin

Uncommon is defined as per the BNF and BNFc standards with the frequency of between 1 in 1000 to 1 in 100. Rare is defined as a frequency between 1 in 10000 and 1 in 1000.

In under 18's, uncommon side effects are anaphylactic reaction, haemorrhage, nausea, vaginal discharge and vomiting.

Idiopathic intracranial hypertension (pseudotumor cerebri) has been reported in paediatric patients receiving the IMP. Participants will be counselled to look out for signs and symptoms of idiopathic intracranial hypertension, including severe or recurrent headache, vision disturbances and tinnitus. If suspected, the PI or delegated clinicians should make an urgent referral to ophthalmology.

In adults, uncommon side effects are alopecia, abnormal appetite, exacerbations of asthma, chills, confusion, constipation, diarrhoea, drowsiness, dyspnoea, flatulence, gout, muscle weakness, altered taste, testicular disorders, tinnitus, vertigo, vision disorders and vomiting.

In adults, rare side effects are abnormal eye sensation, chest pain, difficulty standing, fever, hypotension, influenza like illness, musculoskeletal stiffness, nasopharyngitis, orthopnoea, osteoarthritis and QT prolongation.

8.4 Side effects with unknown frequency of Triptorelin

An unknown frequency is defined as per the BNF and BNFc as that the frequency is not defined by the product literature or that the side-effect has been reported from post-marketing surveillance data.

In under 18's, side effects with an unknown frequency are alopecia, angioedema, epiphysiolysis, gastrointestinal discomfort, headache, hot flush, malaise, myalgia, nervousness, pain, skin reactions, vision disorders and increased weight.

8.5 Side effects of other GnRHa preparations

Leuprorelin acetate has similar side effect profiles to Triptorelin and are detailed in Appendix D.

Those commenced on Leuprorelin acetate and all GnRHa preparations should be counselled on the signs and symptoms of idiopathic intracranial hypertension (such as severe or recurrent headache, vomiting, visual disturbances and tinnitus) and increased risk of depression during use.

They should also be counselled on the signs and symptoms of severe cutaneous adverse reactions (SCARs) as treatment should be immediately discontinued if these occurs.

SCARs is inclusive of Stevens-Johnson Syndrome (SJS) and Toxic Epidermal Necrolysis (TEN) which can be life-threatening or fatal. Signs and symptoms include prodromal illness with fever, malaise, cough, rhinorrhoea, sore throat and sore eyes, an extensive and widespread rash that is itchy and painful with mucosal involvement that is erosive and haemorrhagic.

Rarely, seizures have been reported with GnRHa preparations. Participants with risk factors for seizures (such as a history of epilepsy, and structural brain abnormalities) should be monitored closely.

8.6 Treatment Interactions

There are no known drug interactions with Triptorelin or Leuprorelin acetate.

9 Adverse Event Management and Reporting

All adverse events will be recorded in the participant's medical notes, the study source data worksheets and the eCRF. All Adverse Events and Serious Adverse events will be recorded from the signing of the informed consent form until 12 weeks following the final dose. This reporting period reflects the prolonged pharmacological activity of the 6-month Triptorelin formulation. Events suspected to be related to the IMP occurring beyond this window should also be reported.

SAE's will be additionally reported, within 24 hours of site becoming aware of the event, to the KHP-CTO pharmacovigilance team.

All SAEs, SARs and SUSARs (except those specified in this protocol as not requiring reporting) will be reported immediately (and certainly no later than 24hrs) as per the instructions on the SAE report form. SUSARs will be reported prospectively to the chair of the Data Monitoring Committee (DMC); all other safety events will be listed in DMC reports.

The sponsor will report SAEs and/or suspected unexpected serious adverse reactions as required to regulatory authorities, investigators/institutions, and IRBs/IECs in compliance with all reporting requirements according to local regulations and good clinical practice.

The Medicines for Human Use (Clinical Trials) Regulations 2004 and Amended Regulations 2006 gives the following definitions:

- **Adverse Event (AE):** Any untoward medical occurrence in a participant to whom a medicinal product has been administered, including occurrences which are not necessarily caused by or related to that product.

The electronic version of this document is the latest version. It is responsibility of the individual to ensure that any paper material is the current version. Printed material is uncontrolled documentation.

- Adverse Reaction (AR): Any untoward and unintended response in a participant to an investigational medicinal product which is related to any dose administered to that participant.
- Unexpected Adverse Reaction (UAR): An adverse reaction the nature and severity of which is not consistent with the information about the medicinal product in question set out in the SmPC for that product.
- Serious adverse Event (SAE), Serious Adverse Reaction (SAR) or Suspected Unexpected Serious Adverse Reaction (SUSAR): Any adverse event, adverse reaction or unexpected adverse reaction, respectively, that:
 - results in death
 - is life-threatening
 - required hospitalisation or prolongation of existing hospitalisation
 - results in persistent or significant disability or incapacity
 - consists of a congenital anomaly or birth defect
- Important Medical Events (IME) & Pregnancy: Events that may not be immediately life-threatening or result in death or hospitalisation but may jeopardise the participant or may require intervention to prevent one of the other outcomes listed in the definition above should also be considered serious. Although not a serious adverse event, any unplanned pregnancy will also be reported via the SAE reporting system.

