4.14.8 Adverse Events

During each visit, participants will be asked about adverse events. All adverse events will be recorded in an ongoing adverse event log. Recording of symptom changes is only necessary when treatment is initiated or when the clinician identifies an unusual rate of change. In the immediate arm, there will be an additional telephone visit led by Clinical Nurse Specialists (CNS) or a delegated medical professional, at 3 and 15 months to ask about adverse events that may require discussion with the PI or SI. A researcher will conduct the telephone visits at 9 and 21 months. Within the delayed arm, there will be a parallel researcher-led telephone visit at 3, 9 and 21 months, with a telephone visit at 15 months led by a CNS or delegated medical professional. All telephone check-ins will follow a standardised proforma with clear guidance on escalation to clinical staff if any concerns arise. This ensures consistency in data collection and participant safety, while allowing flexibility in staffing.

The measures included at each assessment point will assess several adverse events (AE) experienced since the last assessment. Systematic enquiry will include, for birth-registered females, breakthrough menstrual bleeding. All participants will be asked about severe and persistent headaches, galactorrhoea, significant weight changes, unexplained pain, persistent nausea or vomiting, and any other physical symptoms that significantly impact the participant's daily functioning. These physical events will be assessed for their severity and potential relation to the study intervention, and appropriate medical interventions will be provided as necessary.

Follow ups will include suicidal thoughts, suicidal behaviour, a marked increase in the severity of anxiety or depression symptoms, defined as T-score on RCADS subscales >80 when previously lower, increased mental distress requiring unplanned clinical appointments and/or A&E attendances. They will also include detailed information on the child's height and weight, prescribed medications, new diagnoses (both neurodevelopmental and mental health, as well as physical health), and the number of GP appointments attended in the past year. It will also cover any planned surgeries or procedures, A&E visits, reasons for these visits, and whether they led to overnight admissions.

Any hospital admission for an overnight stay will be recorded as a serious adverse event (SAE).

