5.6 Discontinuing allocated interventions

Participants may discontinue GnRHa treatment at any time without any detrimental impact on their care. Reasons for discontinuation will be documented, and participants will remain in follow-up according to their randomised arm's schedule of events until the end of the study .

Health care team-initiated discontinuation criteria include:

- Occurrence of any condition that, in the opinion of the Investigator, significantly jeopardizes the wellbeing and safety of the patient, including serious or intolerable AE that prevents the subject from continuing with study participation

The electronic version of this document is the latest version. It is responsibility of the individual to ensure that any paper material is the current version. Printed material is uncontrolled documentation.

- Change in compliance with any inclusion or exclusion criterion that is clinically relevant and affects subject safety, as determined by the Investigator.
- Use of prohibited concomitant medications
- QTc > 470ms
- Pregnancy

When the health care team are considering discontinuation, they will discuss the reasons for this with the participant and their parents/ legal guardians, taking account of their preferences and possible alternative treatment regimes.

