A post-study AE/SAE is defined as any event that occurs outside the AE/SAE detection period. Investigators are not obligated to actively seek AEs or SAEs in former study participants. However, if the Investigator learns of any SAE, including death, at any time after a participant has been discharged from the study, and he/she considers the event reasonably related to the investigational product, the Investigator will promptly notify the Sponsor.

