13.5.2.2.1 TRIAL

Binary secondary outcomes will be analysed using the same approach as the primary analysis. The estimand will be the same as the primary analysis, utilising the treatment policy intercurrent event handling method. The analysis carried out shall use a logistic mixed model, still retaining the fixed and random effect structure of the The electronic version of this document is the latest version. It is responsibility of the individual to ensure that any paper material is the current version. Printed material is uncontrolled documentation.

primary analysis. Uninformative priors will be used for parameters that are to be estimated.

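### Section 9 ties the end of adverse-event recording to the final dose, which conflicts with the protocol's visit schedule, its follow-up of participants who stop, and its 24-month treatment-policy analysis of adverse events

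*Protocol*

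**What the plan says.** Section 9 sets the only explicit start and stop for AE and SAE recording: events "will be recorded from the signing of the informed consent form until 12 weeks following the final dose". It explains the length by the drug: "This reporting period reflects the prolonged pharmacological activity of the 6-month Triptorelin formulation". It adds one exception: "Events suspected to be related to the IMP occurring beyond this window should also be reported". Section 9.2 then builds on this period: "A post-study AE/SAE is defined as any event that occurs outside the AE/SAE detection period".

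Other parts of the protocol have no dose-related end:

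- Section 4.14.8 has participants asked about AEs at each visit, and "All adverse events will be recorded in an ongoing adverse event log". Table 2 lists that log among the ongoing forms to be updated at every visit.
- Section 5.6 says that after discontinuation "participants will remain in follow-up according to their randomised arm's schedule of events until the end of the study". Section 4.8 also asks those who leave their allocated treatment to keep providing data on the Table 2 schedule.
- Section 13.1.7 lists adverse events as a binary outcome. For binary outcomes, section 13.5.2.2.1 says: "The estimand will be the same as the primary analysis, utilising the treatment policy intercurrent event handling method". The primary estimand (13.5.1.1) is set at 24 months and names stopping treatment early, for any reason, as an intercurrent event. Section 13.10.1 analyses everyone as randomised.

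**The concern.** Under a treatment-policy estimand, stopping the drug must not change what is observed. A recording window that closes a fixed time after a person's last dose does change it, because its length then depends on a post-randomisation event.

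The dose calendar makes this unequal between arms. The immediate arm is first dosed at month 0 and the delayed arm at month 12, so an early stopper in the immediate arm would leave the window much earlier in follow-up. For someone in the delayed arm who never starts, there is no final dose from which to count.

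After the window, an event would be kept only if it is suspected to be drug-related. Table 3 lists site staff, treating clinicians and outcome assessors as unblinded. In participants still being dosed, all events count. Ascertainment could therefore differ both by arm and by a causality judgement made with knowledge of allocation. Risk is part of the primary objective, and an analysis plan cannot recover events that were never recorded.

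**Working it through.** The protocol states no figure to reproduce. The check is calendar arithmetic, followed by an illustration under assumed stopping rates.

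**Inputs from the protocol**
- Window: 12 weeks after the final dose (section 9) = 84 / 30.4375 = 2.76 months.
- Doses at months 0, 6, 12, 18 and 24 in the immediate arm (5.2.3). The delayed arm starts at month 12 (5.2.6), then months 18 and 24 (Table 5).
- Endpoint: month 24 (13.5.1.1).

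**Step 1. Unrecorded time per participant who stops**, if section 9 is applied to that person's own last dose:

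unrecorded months = 24 − (month of last dose + 2.76)

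| Last dose | Immediate arm | Delayed arm |
|---|---|---|
| Month 0 | 21.2 | not applicable |
| Month 6 | 15.2 | not applicable |
| Month 12 | 9.2 | 9.2 |
| Month 18 | 3.2 | 3.2 |
| Never dosed | not applicable | no end defined |

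After one injection, the loss is 21.2 months in the immediate arm and 9.2 in the delayed arm.

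**Step 2. Average over an arm.** The protocol gives no discontinuation rate. Assume a probability p of stopping after each dose, equal in both arms, with everyone in the delayed arm starting at month 12. The immediate arm has more dose occasions, so this assumption also gives it more stoppers by month 24.

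Mean loss = Σ p(1 − p)^(k−1) × (unrecorded months after dose k)

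At p = 10%:
- Immediate: 0.100×21.24 + 0.090×15.24 + 0.081×9.24 + 0.0729×3.24 = 4.48 months; 4.48/24 = 18.7%.
- Delayed: 0.100×9.24 + 0.090×3.24 = 1.22 months; 1.22/24 = 5.1%.

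| Assumed p per dose | Immediate, unrecorded share | Delayed, unrecorded share |
|---|---|---|
| 2% | 4.0% | 1.0% |
| 5% | 9.8% | 2.6% |
| 10% | 18.7% | 5.1% |
| 15% | 26.8% | 7.5% |

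The ratio is about 3.6 to 3.9 across this range.

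**Step 3. Illustration for any AE, with no true difference.** Assume a constant rate with a 20% risk over 12 months in both arms: rate = −ln(0.8)/12 per month, so the true 24-month risk is 1 − 0.8² = 36.0%. For those who stop, the recorded risk is 1 − 0.8^(t/12), where t is the month the window closes: 5.0% at 2.76, 15.0% at 8.76, 24.0% at 14.76 and 32.0% at 20.76. At p = 10%:
- Immediate: 0.100×5.0 + 0.090×15.0 + 0.081×24.0 + 0.0729×32.0 + 0.6561×36.0 = 29.8%.
- Delayed: 0.100×24.0 + 0.090×32.0 + 0.810×36.0 = 34.4%.

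The gap is 4.7 points before rounding, with fewer events recorded in the immediate arm. The same calculation gives 2.5 points at p = 5% and 1.0 point at p = 2%. All these figures assume that nothing is recorded after the window and that stopping is unrelated to having had an event.

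**Step 4. After the fix.** With recording to the later of month 24 and the end of the post-dose window, unrecorded time before month 24 is 0 in both arms.

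**The case against.** A reader might infer that AE data after stopping will be lost, that the treatment-policy contrast is therefore unobtainable, and that immediate treatment will be made to look safer. The documents do not support that, for these reasons:

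- **Other sections require collection.** Section 4.14.8 and the ongoing log in Table 2 apply at every visit, and participants who stop keep their visits. A site following those sections loses nothing. This stands, and it makes the point a conflict between rules rather than a certain loss.
- **Suspected drug-related events stay reportable after the window.** This stands. Only events judged unrelated are exposed. It does not remove the problem, because the judgement is made by unblinded staff and is not needed for participants still being dosed.
- **The release in section 9.2 from actively seeking events is worded for former participants.** Someone who has stopped the drug but remains in follow-up is not clearly one of these. This stands, although section 9.2 still labels as post-study any event outside the detection period.
- **Final dose may mean the last scheduled injection.** The MRI window in Table 2 and section 4.17 refers to the final treatment in this way, around month 24. On that reading recording runs past month 24 in both arms. The reading is possible, but section 9 does not say so.
- **The illustration overstates the effect if stopping follows an AE.** Such a participant already has an event recorded, so a yes/no outcome cannot be changed by later truncation. This stands.
- **Other harm measures do not depend on this window.** Hospitalisations, the suicide screen, anxiety and depression scores, bone density, blood pressure and bloods are separate outcomes on the visit schedule. This stands and limits what is at stake to the AE and SAE records.

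**Conclusion.** The point holds as an internal contradiction. Section 9 gives a recording period that, applied to each participant's own last dose, cannot be squared with sections 4.8, 4.14.8 and 5.6, Table 2, or the 24-month treatment-policy analysis of adverse events. The calendar result is firm on that reading: up to about 21 months unrecorded in the immediate arm and about 9 in the delayed arm after a single dose, for events judged unrelated, with no end defined for delayed-arm participants never dosed.

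The arm-level shares and the gaps of 1.0 to 4.7 points are illustrations only. They rest on assumed stopping and event rates, on section 9 prevailing at every site, on no capture of suspected-related events after the window, and on stopping being independent of earlier events. The nearest figure in the protocol, 0 to 8% desisting from treatment and a transitioning pathway (section 1.2.2), is a different quantity. No size or certainty of bias can be claimed. What can be said is that sites may follow different rules, and that under the literal rule ascertainment ends earlier for immediate-arm participants who stop early. It should be corrected before data collection depends on it.

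**What to change.** Reconcile the passages in section 9: all AEs and SAEs are recorded for every randomised participant from consent to the later of the month-24 visit and the end of the post-dose window, whether or not dosing has stopped or ever started. Keep the existing sentence on later events suspected to be drug-related. In section 9.2, define post-study as after that date.

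This changes no dose, schedule or clinical rule, and the length of the post-dose window can stay as it is. The visits, telephone check-ins and AE log to month 24 already exist for these participants. The cost is a protocol wording change and a few more events to enter.
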